6.2. Recruitment and enrolment

The recruitment of potential subjects will commence only once authorisation has been received from the respective Ethics Committee. Recruitment will occur through competitive enrollment in UK. The recruitment period from first subject enrolled to last subject enrolled will be approximately 12 months.

Recruitment will be via admitted patients in recruiting sites with hospitals, outpatient clinics, community collaborations, subject screening visits or subject records kept at the participating sites and advertisement in paper form and/or digital platforms.

6.2.1. Screening of potential subjects

If a subject is potentially eligible and interested in participating, written information about the investigation (Patient Information Sheet) will be provided to the subject to ensure they are given the opportunity to understand what the investigation is about. Subjects will have time to ask the PI, or delegate, any questions they may have. The subject information provides information to subjects about how to contact the local Principal Investigator or a representative thereof if they wish to learn more about the investigation.

For subjects with more than one eligible wound, only a single wound can be included in the investigation.

If a potentially eligible subject is interested in participating in the investigation a screening visit will be arranged. When arranging the visit, the subject must receive the Patient Information Sheet and given adequate time to review it. The subject will receive both written and verbal information about the possibility of bringing a companion to the visit and to any possible subsequent visits.

The subject has the right to wait before deciding to participate. If/when the subject decides to participate, he/she will be asked to sign the Informed Consent Form If a subject so desires, and it is certain that it is understood what the investigation entails, and the Informed Consent Form has been signed, the subject is considered enrolled/included in the investigation.

The clinical monitor will have close contact with each site during the recruitment period. The PI, or delegate, at each site will notify the clinical monitor when a subject is enrolled and all future planned visits.

Sites will recruit subjects with both VLU's and DFU's. The subject will be stratified according to wound type. It is not required to have an equal number of subjects with VLU's and DFU's. When the Coloplast Clinical Manager becomes aware that 100 subjects have been included and randomised, the recruitment will stop. If, at this time, there are subjects who have been informed of the investigation and are reflecting on participation, they will be given the opportunity to be included within the first 24 hours hereafter.

6.3. Subject withdrawal criteria

A subject can withdraw from the investigation at any time for whatever reason without any consequences for their future treatment outside the clinical investigation. The Investigator may withdraw a subject from the investigation at any time if they judge it to be in the subject's interest.

The investigator must withdraw a subject from the investigation due to:

- Major noncompliance with the Clinical Investigation Plan (CIP) impacting the scientific integrity
 of the investigation.
- If subject's safety and wellbeing is compromised by further participation.
- Subjects lost to follow-up. At least three documented attempts of contact (phone and/or written) will be made to verify subjects lost to follow-up.

6.4. Point of enrolment

A subject is considered enrolled/included in the investigation when written informed consent is obtained.

6.5. Screening Failures and randomisation failures

Subjects that have signed the informed consent form but fail to comply with inclusion or exclusion criteria are considered screening failures.

A subject can be randomized by mistake e.g., if the investigator realizes that the subject is not eligible after the subject has been randomised. If the subject has not started study treatment and has no data registered on endpoints the subject can be replaced by a new subject if the new subject can complete the investigation within timelines (before last subject last visit and within visit windows).

If a subject is randomized to one product but by mistake gets the opposite product it will be regarded as a randomization failure. As this is an exploratory investigation the statistical analyses will in that case be based on the actual product and not the randomized product.

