5.8. Randomization Procedure

All included subjects that meet the inclusion and exclusion criteria will be randomized to one of two treatment groups. Randomization will be centralized using Medidata RAVE and stratified based on wound type (VLU or DFU).

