5.9. Blinding

No blinding will be used in this investigation, as it is not possible to blind the products due to visible differences. The trial statistician will be blinded until database lock to ensure decisions related to data before database lock do not affect the final results.

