6.1.1. Inclusion criteria

Table 2: Inclusion criteria

clus	ion criteria	Justification			
1.	Has given written consent to participate by signing the Informed Consent Signature Form	To meet Helsinki declaration			
2.	Is at least 18 years of age and has full legal capacity	To meet Helsinki declaration			
3.	Has a venous leg ulcer (VLU) (C6 of the CEAP classification(1)) or a non-infected diabetic foot ulcer (DFU) with a duration longer than 8 weeks but no longer than 24 months (Appendix 4)	VLUs and DFUs are some of the most prevalent chronic wounds, they are both categorized as hard to heal ulcers and are most likely to require filler and secondary dressing due to exudate levels and dimensions of the wounds. To ensure reasonable recruitment time, both wound types will therefore be included in the study, and stratification will be made to ensure equal distribution of both wound types in the two arms			
4.	Has a wound with depth ¹ down to 20 mm	To comply with product specification of Biatain ® Silicone in terms of conformability			
5.	Has a maximum wound depth ¹ relative to wound diameter ² with specifications presented in table 1	To quantify conformability, it is essential to ensure that the dressing can conform relative to the width of the wound, which means how the foam increases in height (the swelling rise), when exposed to wound fluids, relative to the diameter of the wound. In Coloplast, the definition of a wound bed conforming dressing is defined as a dressing that conforms to an Alpha (α) value of 0.2, which is also the lower specification limit for Biatain® Silicone (18). However swelling rise has demonstrated to reach maximum of ~ 2 cm in tests with fence sizes (simulated wound diameter) ≥ 6 cm (19). Thus, wound-α is therefore not relevant for these wounds in this study due to inclusion criteria #4.			
6.	Has a wound with exudate levels requiring a filler and a standard secondary dressing	To include wounds that would normally require the comparator dressing regime and ensure that the treatment is aligned with the indications of the dressings			

7.	Has acceptance of compression therapy in case of a VLU or off-loading in case of a DFU, according to local standards	To ensure optimal conditions for wound healing, compression therapy must be performed for VLUs, according to standard of care. For DFUs, off-loading must be performed according to standard of care based on subject need (wound location), preference and resources available

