6.1.2. Exclusion criteria

Table 3: Exclusion criteria

clus	sion criteria	Justification
1.	Wound is infected. For DFUs, has infection severity mild-severe according to the IWGDF/IDSA guideline (Appendix 5). For VLUs, has 2 or more clinical signs of infection as defined in protocol, based on clinical judgement by investigator/tissue viability nurse (Appendix 6)	Anti-microbial dressings are usually used for infected wounds in this study setting, according to recommendation. For identification of infection in DFUs, the validated IWGDF/IDSA system will be used. No similar validated scoring system currently exist for VLUs. For this reason, clinical signs are used as an indicator of infection according to clinical practice; The presence of 2 or more clinical signs of infection, will exclude subjects with VLUs from participating in the study.
2.	Wounds is with exposed tendons, is with bones or has fistulas	Complicated wounds which may require different treatments and have different healing patterns
3.	Wound is with cavity, or is undermined or tunnelling	Due to potential depth of wounds
4.	Subject is receiving chemotherapy	The skin undergoes major changes because o radio- and/or chemotherapy, and therefore it can be more fragile during wound management.
5.	Subject has ankle-brachial pressure index (ABPI) below 0.8 (measured at a frequency according to local standards)	Compression therapy is contraindicated in subjects with low ABPI
6.	Wound is larger than 10 x10 cm	Larger wounds are likely to have a higher %- area reduction which may cause bias in the overall sample size.
7.	Currently enrolled in another wound care device investigation unless co-enrolment has been agreed with the sponsor	To avoid bias

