10.1. Statistical design, method, and analytical procedures

The primary objective will be evaluated by analyzing the primary endpoint whereas the analyses of the exploratory endpoints will be used to further evaluate and explore the primary objective. The secondary objective will be evaluated by analyzing the secondary endpoint.

All baseline measurements, endpoints and assessments will be summarized by descriptive statistics and/or listed. Descriptive statistics for continuous variables are presented with N, Mean, SD (standard deviation), Median, Min and Max, where N denotes the number of subjects contributing with non-missing data. For discrete variables, descriptive statistics are presented with N and percentage, where percentage is based on the total number of subjects/observations with non-missing data.

As it is an exploratory study no adjustment for multiple testing will be applied.

All statistical analysis will be performed with SAS (version 9.4/Enterprise Guide version 7.1)

Definition of analysis populations:

The Intention to Treat (ITT), Safety and Per Protocol (PP) populations will be defined at a formal data review meeting before data base lock. As a minimum, the data manager, the clinical manager, the scientific manager, and the statistician will be involved in the classification of subjects according to the below described criteria.

The ITT population (full analysis set) will be constituted by all randomized subjects with valid informed consent who have been exposed to at least one product.

The PP population will constitute a subset of ITT subjects who:

· fulfill the inclusion/exclusion criteria

- have not used other dressings than the investigational test product(s) during the study period
- Have not had a wound infection during the study period
- have not shifted therapy during the study period

Any exclusion of subjects from the ITT/PP populations must be documented.

Invalid individual datapoints may be omitted from the analysis even though the corresponding subject is part of the ITT/PP populations. Any exclusion of data points will be documented

The Safety Population will constitute by subjects who have given informed consent.

All statistical analysis will be based upon the ITT and PP populations, whereas adverse events and device deficiencies will be assessed based on the Safety population.

Considering the data obtained, it may be considered to make additional explorative analysis, based on a subset of ITT/PP populations.

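### Sections 6.5 and 10.1 let a randomised subject who has not yet been dressed leave the ITT set after the investigator knows the arm, on eligibility criteria that partly rest on judgement

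*Combined protocol and SAP*

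**What the plan says.** Section 6.5 gives this as an example of a randomisation error: "A subject can be randomized by mistake e.g., if the investigator realizes that the subject is not eligible after the subject has been randomised". The consequence is: "If the subject has not started study treatment and has no data registered on endpoints the subject can be replaced by a new subject", provided the new subject can finish within the trial's timelines.

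Section 10.1 defines the ITT population, which it also calls the full analysis set, as "all randomized subjects with valid informed consent who have been exposed to at least one product". Exclusions must be documented, and the populations are settled at a data review meeting before database lock.

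Section 5.9 states: "No blinding will be used in this investigation". Only the statistician is kept blind, until lock.

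Section 7.2 lists the V1 steps: eligibility check, baseline data with photo, depth and wound assessment, randomisation in Rave, then application of the allocated dressing. Table 4 in section 7.3 assigns randomisation to the investigator or delegate.

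Among the criteria, inclusion 6 reads "Has a wound with exudate levels requiring a filler and a standard secondary dressing", with no threshold. Infection of a venous leg ulcer under exclusion 1 is decided "based on clinical judgement by investigator/tissue viability nurse". Exclusion 3 removes wounds with a cavity, a term the plan does not define, although depth down to 20 mm is allowed.

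**The concern.** An ITT analysis is protected by randomisation as long as staying in the set does not depend on the arm. Here the person who can decide that a subject was never eligible has just seen the allocation. Sections 6.5 and 10.1 do not ask for a reason that existed on record before allocation, or for a decision by someone unaware of the arm.

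The criteria leave room for second thoughts. Need for a filler and presence of a cavity have no numeric limit. Appendix 6 counts delayed or absent healing as one of the seven signs of venous ulcer infection, two of which exclude. Every eligible ulcer is older than 8 weeks, so many arguably show one sign already, and a single further sign would change the decision.

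The arms also differ in the feature under judgement: inclusion 6 selects wounds thought to need a filler, and only the comparator arm supplies one. The same wound could therefore be reconsidered for different reasons in each arm. At stake is whether the set labelled ITT still gives a randomised comparison of wound area reduction, the first part of the success rule in section 10.4.

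**Working it through.** **1. Is the arm known when the rule applies?** Yes. Randomisation and dressing are consecutive steps at V1 (section 7.2), site staff perform the randomisation (section 7.3) and they are not blinded (section 5.9). Central randomisation (section 5.8) conceals the allocation beforehand but does not prevent removal afterwards.

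**2. What does the condition on endpoint data do?** There are two readings.
- Strict: baseline photo, depth and wound assessment are listed before randomisation, and Appendix 9 marks V1 for wound depth and wound condition. Endpoint data then already exist for almost everyone, and replacement is nearly impossible.
- Post-baseline data only: replacement is open for any randomised subject found ineligible before dressing.

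On either reading, the exposure condition in section 10.1 still removes an undressed subject from ITT.

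**3. Do the existing safeguards close the gap?** Section 10.1 requires exclusions to be documented, but not reported by arm. Section 9.4 verifies inclusion and exclusion criteria at 100%, but for timely completion. The data review meeting comes after the removal. None of these makes the decision independent of the arm.

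**4. How large could the effect be?**

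Plan inputs (sections 6 and 10.2): SD of wound area reduction 43 points, 40 completers per arm, 20% dropout, total 100. The plan's total reproduces: 80 / (1 − 0.20) = 100. Barring replacement would not change it. Fifty per arm is implied by the equal completer numbers; no allocation ratio is stated.

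Expected half-width of the 95% interval for the difference, with t(0.975, 78 df) ≈ 1.991:
1.991 × 43 × √(2/40) ≈ 19.1 points.

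Assumptions, not in the documents: k of 50 subjects in one arm are selectively replaced within that arm, and the removed and replacing subjects differ by D points in expected wound area reduction. The shift in the arm mean is k × D / 50.

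| k | D = 20 | D = 43 (1 SD) | D = 60 |
|---|---|---|---|
| 1 | 0.40 | 0.86 | 1.20 |
| 2 | 0.80 | 1.72 | 2.40 |
| 3 | 1.20 | 2.58 | 3.60 |
| 5 | 2.00 | 4.30 | 6.00 |

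As a share of the half-width, k = 2 with D = 43 gives 1.72 / 19.1 ≈ 9%. The extreme corner gives 6.0 / 19.1 ≈ 31%, but needs one subject in ten in that arm to be removed.

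Sensitivity: with 40 analysed per arm, k × D / 40 runs from 0.5 (k = 1, D = 20) to 7.5 (k = 5, D = 60), and k = 2 with D = 60 gives 3.0. Section 6.5 does not say that the new subject takes the same arm. With no same-arm replacement, and D measured from the full-arm mean, k × D / (50 − k) runs from 20/49 = 0.41 to 300/45 = 6.67.

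**The case against.** The strongest reply is that the opening is narrow. Eligibility is verified at V1 before randomisation, section 5.8 randomises only subjects who meet the criteria, and dressing is the next listed step. The strict reading of the endpoint-data condition leaves replacement almost no use. A clinician uneasy about a wound also has another route: sections 5.1 and 7.5 let the dressing regime change while the subject stays in follow-up and in ITT. And not every criterion is loose: depth is numeric against Table 1, diabetic foot infection follows the grading in Appendix 5, and venous ulcer infection uses a checklist. All of this stands, and it limits how often the rule could matter. It does not remove the opening. The alternative route is for a subject already in treatment, and the exposure condition works even where replacement is blocked.

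A reader might infer more: that deep or wet wounds would be lost from the Biatain Silicone arm, raising its mean area reduction, lowering its dressing count and so favouring both parts of the section 10.4 rule. The documents do not support this. Table 1 allows 20 mm depth only at diameters of 6 cm or more, and the justification for exclusion 6 says larger wounds are likely to show a higher percentage reduction. On that premise, losing the deepest wounds could lower the arm mean. Second thoughts are possible in the comparator arm too: section 4.8 describes AQUACEL EXTRA for moderately and highly exuding wounds, so a drier wound might be reconsidered there. No figure in the plan allows an effect on cost to be sized.

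**Conclusion.** The point holds as a weakness in the rules. Sections 6.5 and 10.1 together permit exclusion from ITT by someone who knows the arm, on criteria that are partly judgement, with no required basis in pre-randomisation facts. The number of such cases is unknown, and the direction of any bias cannot be established from the documents. With one or two cases in an arm, the assumed range is 0.4 to 2.4 points on 50 subjects, or up to 3.0 points on 40, which is at most about a sixth of the expected half-width of 19.1 points. These sizes rest on the assumed k and D and on equal arms. Because section 10.4 gives no margin for comparable performance, no particular shift can be said to change the conclusion. This is a cheap improvement, not a flaw that threatens the trial.

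**What to change.** - **Section 6.5:** allow replacement, or exclusion from ITT, only when a value or fact recorded before randomisation shows that an eligibility criterion was not met. State that data registered on endpoints means post-baseline data.
- **Before randomisation:** require the completed eligibility form, including inclusion 6 and exclusions 1 and 3, to be signed before Rave releases the allocation. The documents do not describe the Rave configuration, so this may already be in place.
- **Section 10.1:** keep every other randomised, consenting subject in ITT whether or not a dressing was applied, and follow them to V5 where possible. Section 5.1 already asks withdrawn subjects to complete the termination visit.
- **Report:** list all post-randomisation removals and all undressed subjects by arm, with reasons.

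The cost is wording in two sections and, if needed, one system check. The sample size and treatment rules do not change. The downside is that a few undressed subjects, some without a week-4 area, stay in the ITT set.

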4.7. Total number of test products intended for the clinical investigation

The subjects will be included for 4 weeks of investigation. On average, it is expected that subjects will require 1-3 dressing changes/week. Therefore, each subject is expected to use a maximum of 12 products during their participation.

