7.2.2. Dressing changes between site visits

If the wound requires frequent dressing changes (more than once scheduled visit per week), unscheduled visits at the site can be scheduled for dressing changes.

The dressing change can also take place at the subjects home by the subject or by a homecare nurse. The subject will be provided with the additional study products to which he/she is allocated at each visit to use at home in case of additional dressing changes in between visits. An information sheet for the homecare nurse will be distributed to the subjects to be shared with the homecare nurse, providing information about the study and the study treatment to ensure that the protocol is followed between scheduled visits.

In the event of a completed dressing change between the weekly scheduled visits, it must be documented at the next scheduled weekly visit in the eCRF to capture the total number of dressings since last scheduled visit. The subject will be instructed to complete a sheet for dressing changes between the scheduled weekly site visits capturing the dressing change and date of the event.

No clinical investigation-related wound assessments are conducted during the unscheduled visits and/or dressing changes at the subjects home. Cleansing of wound must be done according to standard of care and debridement, if needed. The dressing applications between weekly scheduled visits must be according to randomization.

The total number of dressings, the sizes of the dressings used and frequency of dressing changes per subject is part of the cost-effectiveness analysis.

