10.4. Pass/fail criteria

The purpose of this investigation is fulfilled if the performance of the products in the two arms is comparable in terms of wound area, while the mean total cost for Biatain® Silicone is significantly lower than for Standard of Care.

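### Section 6.5 groups mis-allocated subjects by product received even in the analysis labelled ITT (small expected effect); separately, the week-4 model has no rule for missing areas and leaves the V2–V4 areas unused

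*Combined protocol and SAP*

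**What the plan says.** **Grouping.** Section 6.5 calls it a randomisation failure when a subject is randomised to one product and by mistake gets the other. Because the study is exploratory, "the statistical analyses will in that case be based on the actual product and not the randomized product". Section 10.1 states that "All statistical analysis will be based upon the ITT and PP populations". It defines ITT by membership: "The ITT population (full analysis set) will be constituted by all randomized subjects with valid informed consent", with exposure to at least one product. Neither section says that ITT subjects are compared as randomised.

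Section 10.4 nevertheless sets a success criterion with two conditions. The first concerns healing: "The purpose of this investigation is fulfilled if the performance of the products in the two arms is comparable in terms of wound area". The second asks that the test arm's average dressing cost be lower than the comparator's at the significance level. Section 10.3 sets a two-sided 5% level.

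**Missing areas.** Section 10.1 analyses percent wound area reduction (WAR) with treatment and wound type as fixed effects and baseline area as covariate, and has no visit term. Section 10.2 takes the endpoint from baseline to week 4, sizes the study on 40 completers per arm and allows for 20% loss. Week 4 is named only there; sections 5.2 and 10.1 do not name the analysis visit, and Appendix 9 ticks V2 to V5 for the primary endpoint. Section 5.7 has the wound photographed at every scheduled visit. Section 5.1 requires a Termination visit from withdrawn subjects, and section 7.2 places V5 at day 28, with a window of two days before.

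**The concern.** An analysis called ITT should keep each subject in the arm that randomisation assigned. Moving a subject to the other arm because of an error made after randomisation gives up that protection if errors are related to prognosis. Both conditions in section 10.4 are comparisons between the two groups, so both depend on how the groups are formed. The word exploratory sits badly beside a pass/fail rule.

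The second matter is a gap and not an error. A single-value analysis of covariance drops a subject with no week-4 area. If poorly healing subjects leave one arm more than the other, the difference among those who remain is biased. Areas from the earlier visits are collected and could carry some of the missing information, but the planned model does not use them. The plan also does not say whether the area from an early Termination visit counts as week 4.

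**Working it through.** **Inputs from the plan:** SD of WAR 43 points, 40 completers per arm, 20% loss, 100 randomised (section 10.2). Everything else below is an assumption, marked as such.

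**1. The plan's own figures.** Enrolment: 80/(1 − 0.20) = 100, which reproduces. Half-width of the 95% CI for the difference at the planning SD: t(0.975, 78) × 43 × √(2/40) = 1.991 × 9.615 = 19.1 points. With 50 per arm it is 17.1. (The chance of a half-width below 21 computes to 0.894 for the difference, and the chance of one below 15 for a single arm to 0.806. Section 10.2 states 80% and 89%, so the two look transposed. This does not affect N = 100 or this point.)

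**2. Shift from grouping by product received.** Let k subjects, all in one direction, have outcomes g points worse than their randomised arm's mean. Moving them shifts the difference by k·g/(n − k) + k·g/(n + k). Both k and g are assumed.

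| n per arm | k | g = 10 | g = 30 |
|---|---|---|---|
| 50 | 1 | 10/49 + 10/51 = 0.40 | 1.20 |
| 40 | 1 | 10/39 + 10/41 = 0.50 | 1.50 |
| 50 | 3 | 30/47 + 30/53 = 1.20 | 3.61 |

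One error is therefore about 2% to 8% of the 19.1-point half-width (0.40/19.14 to 1.50/19.14). If errors are balanced or unrelated to prognosis, the expected shift is 0.

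**3. Cost of grouping as randomised.** With k one-way errors among 50, a true difference shrinks by the factor 1 − k/50, or 2% per error. The plan gives no power for the cost test. If it were 80% (noncentrality 2.80, normal approximation), it would become 78.4% with one error (2.80 × 0.98) and 75.0% with three (2.80 × 0.94).

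**4. Missing week-4 areas: simple bound.** If 20% of one arm is missing and the missing mean differs from the observed mean by an assumed d, the completers' difference is off by 0.20 × d: 2.0, 4.0 or 8.6 points for d = 10, 20 or 43.

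**5. Missing week-4 areas: simulation.** Assumed: 4,000 trials per case; 50 per arm, 10 leaving per arm (4/3/3 after weeks 1/2/3); SDs 20/30/37/43; adjacent-week correlation 0.6, 0.8 or 0.9; maximum likelihood with pooled slopes and no covariates. This is simpler than the model recommended below, so it is a guide to size only.

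- Random exit: no bias. SE for completers 9.65/9.55/9.72, likelihood-based 9.47/9.15/9.10, which is 1.9%, 4.2% and 6.4% lower.
- Equally selective exit in both arms: completers within 0.31 points of zero.
- Slow early healers leave one arm only: completers off by 1.7 to 6.8 points, likelihood-based within 0.16 of zero (missing at random was built in).
- Exit in one arm depends on the unseen week-4 value: completers off by 4.5 to 8.5 points, likelihood-based still off by 1.8 to 6.9.

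**6. Early Termination area read as week 4.** Assume exits spread evenly over weeks 1 to 3. With mean WAR 10/20/30/40 the average deficit is (30 + 20 + 10)/3 = 20; with 20/30/36/40 it is (20 + 10 + 4)/3 = 11.3. Exits of 12 v 8 give 20 × 4/50 = 1.6 and 11.3 × 4/50 = 0.9 points; 10 v 10 gives 0.

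**The case against.** Section 6.5 is prespecified, disclosed and reasoned, and section 10.1 defines ITT only by who is in it, so the two sections do not contradict each other. That is true, but it leaves the ITT label inaccurate for these subjects.

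As-randomised grouping pulls a true difference towards zero and so favours a comparability claim. This stands, and it is why the as-received analysis should be kept as a sensitivity analysis.

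Errors should be few, since section 5.8 centralises randomisation, and the effect per error is small. This also stands.

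A reader might infer that PP keeps mis-allocated subjects in. That PP subjects "have not used other dressings than the investigational test product(s) during the study period" could be read to cover both arms' products. But section 10.1 also bars subjects who changed therapy during the study, which on a natural reading removes anyone who used both. Only a subject on the wrong product throughout is left unclear.

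A reader might also infer that the product received will often be ambiguous, because "it is expected that subjects will require 1-3 dressing changes/week" and "The dressing change can also take place at the subjects home by the subject or by a homecare nurse". Section 7.2.2, however, supplies subjects with their allocated product and requires changes between visits to follow the randomisation. Nothing suggests that mixed use is expected.

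Nor does section 6.5 regroup subjects whose dressing is changed for clinical need; section 7.5 keeps them in ITT.

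On missing data, the plan limits losses through continued follow-up and the Termination visit, and the pre-lock review and blinded statistician limit data-driven choices. None of these supplies a rule, and a Termination visit cannot be counted on for a subject lost to follow-up. Choosing a mixed model is partly preference.

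**Conclusion.** The grouping rule is wrong as written for an analysis labelled ITT, with a small expected effect: about 0.4 to 1.5 points per error against a half-width of about 19.1, and zero on average if errors are unrelated to prognosis. The prognosis gap of 10 to 30 points and the number of errors are assumptions.

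It would be tempting to conclude that the rule could change the trial's outcome. The documents do not support that: section 10.4 gives no comparability margin, so no shift can be shown to change the decision.

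The missing-area matter is a cheap improvement. The completers-only reading is implied by the single-value model and the sizing on completers; the plan does not state it. The dropout biases of several points should not be read as predictions. They need selective exit that differs between arms, they rest on inputs the plan does not give, and the simulation did not fit the recommended model.

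**What to change.** **Grouping.** Replace the section 6.5 sentence with: *ITT analyses of wound area and cost use the randomised product; subjects given the opposite product are excluded from PP; analysis by product received is reported as a sensitivity analysis.* A one-line definition of product received would settle any rare mixed case.

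**Missing areas.** Analyse WAR at V2 to V5 in a repeated-measures mixed model with treatment by visit, wound type, baseline area by visit and an unstructured covariance. Report the week-4 difference with its 95% CI. Place any Termination area taken before the V5 window at the week it was taken. Keep the week-4 analysis of covariance as a sensitivity analysis.

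**Cost.** Wording changes and a standard SAS procedure; no new visits or data. The mixed model assumes data are missing at random, so it only partly corrects exit that depends on unseen week-4 values. It cannot use a subject with no area after baseline.
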